9.1.1 Rationale for Including Selected Exposure Variables

Age and sex are associated with suicidal ideation and behavior.³⁰ Adults over 35 years old are more likely to die by suicide than other age categories.²⁵ CDC reports that suicidal completion is approximately 4 times more common among males than females.²⁵ The age/sex distribution of suicidal ideation and behavior differs from that of suicidal completion. Routine data from 492,797 patients seen in SLHS EDs

and primary care clinics (SLHS data) indicate that in this population, the likelihood of screening positive for suicidal ideation or behavior is similar among adult females and adult males (2%) but is twice as common among adolescent females (8%) as among adolescent males (4%).³⁴ Overall, adolescents in this population experience higher rates of suicidal ideation (6%) than adults (2%).³⁴ The scientific literature is limited regarding the effect of safety planning with adolescents. We hypothesize that age may moderate the effect of the comparators on outcome variables and may differ for suicidal adult versus adolescent participants; **the current study will be powered to report results stratified by agecategory.**

Gender identity and sexuality are strongly associated with risk of suicidal ideation and behavior. **Lesbian, gay, bisexual, transgender, or gender-nonconforming (LGBTQ+) individuals are two to seven times more likely than straight, cisgender peers to attempt suicide.**³⁵⁻⁴⁰

Race and ethnicity are also associated with each of the baseline characteristics. **The rate of suicide is approximately three times higher among Non-Hispanic Whites and American Indian/Alaska Natives (16.71 and 18.37 per 100,000 respectively) than among other racial and ethnic groups.**²⁵

Religious affiliation is associated with suicidality, but the magnitude and direction of that association differs depending on the religion and its intersection with socio-cultural factors (e.g., sexuality). A recent meta-analysis found that **religiosity protects against suicidal completion**, with a pooled odds ratio of 0.38 (95% CI: 0.21-0.71).⁴¹ Another review found that 75% of published studies identified religion as protective against suicidal ideation and behavior.⁴²

The Health Resources & Services Administration's Federal Office of Rural Health Policy urban-rural designation for census tracts⁴³ will be used together with patients' home addresses to classify study participants as urban or rural residents. Compared to large urban areas, **rural residence is associated with a 45% higher rate of suicide,²⁵ lower socioeconomic status,⁴⁴ and worse overall health outcomes.**⁴⁴ Thirty-five of Idaho's 44 counties are classified as rural⁴³ and we have included study sites serving urban and rural residents. Geographic location and urban/rural location were included as matching criteria in order to ensure an equal distribution of rural clinics in intervention groups.

Financial crises and low socio-economic status (SES) are associated with an increase in suicidality.³ The study will collect data related to SES including income, education, and employment through a Baseline Survey using standard questions from the US Census Bureau's 2019 American Community Survey.⁴⁵

Health-related quality of life is a key predictor of overall physical and mental wellbeing. Quality of life will be measured at baseline using the Euro-Qol tool (EQ-5D-5L for adults and EQ-5D-Y for adolescents).² The EQ-5D-5L is a five-question survey that includes five dimensions (mobility, self-care, usual activities, pain/discomfort, and anxiety/depression). Many physical and behavioral comorbidities and use of certain medications are associated with suicide risk. A recent study found that at least occasional

marijuana use and alcohol use among adolescents with suicidal ideation are associated with an increase in suicide attempts.⁴⁶

9.2 Primary Outcome & Assessment

The primary outcome of interest (suicidal ideation and behavior) and the secondary outcomes (loneliness, uptake of outpatient mental healthcare services, and ED utilization for suicidality) were selected because these are the outcomes that people with lived experience with suicide (PLES) and the Provider Advisory Board (PAB) indicated were most important to patients, caregivers, and providers.

Outcomes will be measured at baseline (immediately prior to study enrollment as part of usual care for all patients (suicide risk) or immediately following study enrollment (loneliness)), and at 6 months (+/- 4 weeks), and 12 months following study enrollment (+/- 4 weeks).

Aim 1: The primary outcome is reduced suicidal ideation and behavior (measured as change from baseline score at 6 and 12 months using the Columbia Suicide Severity Rating Scale (C-SSRS)).^{1,15,16,47} The C-SSRS is widely used in practice and research, and has strong psychometric properties for use with both adult and adolescent populations, which are summarized in a *Supporting Evidence* document.¹⁶ The C-SSRS was developed in American English and has been translated to multiple languages; the Spanish language version has been validated.^{16,48} The C-SSRS has been shown to be an effective tool to measure suicidality (diagnosis) and is sensitive to change over time, which allows measurement of the effect of treatment at 6 and 12 months.^{16,49}

The C-SSRS is available in a full-length version comprised of 11 yes/no questions plus 7 multiple choice questions and space to collect and record brief narrative explanations. An abbreviated screener version of the C-SSRS consists of 5 yes/no questions related to suicidal ideation and one two-part yes/no question related to suicidal behavior. Both the full-length and screener versions of the C-SSRS are available in a 'lifetime-recent' version (to establish a baseline) and a 'since last contact' version to be administered at follow-up visits. Two versions of the C-SSRS will be used for this study: C-SSRS Lifetime-Recent Screener (given at baseline, in accordance with standard of care at SLHS), and C-SSRS Since Last Contact Screener (given at 6 and 12 months). In addition to using the C-SSRS Screeners at baseline and follow-up, the study will incorporate three items from the full-version of the C-SSRS that are not included in the screener version to measure: (1) Aborted or self-interrupted suicide attempts; (2) interrupted suicide attempts; and (3) actual suicide attempts at baseline, 6, and 12 months. Non-lethal self-harm, lethal means used for attempts or completions, and death by suicide will also be collected. Vital records will be used to measure suicide completion.

In EDs, C-SSRS screening is routinely administered by nurses during triage as standard of care, while in primary care clinics the C-SSRS screener will be self-administered by patients. The C-SSRS delivered as standard of care in either setting will be used as the basis for determining eligibility for completing a safety plan and eligibility for study enrollment. However, in ED settings, the C-SSRS will be re-

administered in a self-complete format for study participants as part of their baseline surveys, from which change in severity of suicidality will be measured when they self-complete the C-SSRS as part of 6 and 12-month outcome surveys.

The two C-SSRS scores collected during the baseline visit in EDs (nurse-administered vs. self-administered) will be compared as a sub-analysis to assess for any systematic differences in score. The results of this sub-analysis may inform future clinical practice as it relates to C-SSRS administration in SLHS EDs and other settings.

Table 3: C-SSRS Screening Tools by Timepoint, SPARC Trial

Timepoint	C-SSRS Assessment Used
Baseline Survey	Lifetime-Recent C-SSRS Screener (6 questions)
6- and 12-month Outcomes Survey	Since Last Contact C-SSRS Screener (6 questions)

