6.1.2 Study Participant Inclusion & Exclusion Criteria

Inclusion criteria are intentionally broad, to facilitate recruitment of a study sample that is maximally representative of the population of patients that SLHS serves.

Inclusion Criteria

- Patient at SLHS ED or primary care study site
- ≥ 12 years of age (adult ≥18 years of age or adolescent 12-17 years of age)
- Positive screen for suicidal ideation or behavior using C-SSRS (any C-SSRS score >0), or current /most recent visit is related to suicide attempt
- Completed safety plan or connection & support plan as part of current/most recent visit
- Access to a phone (cellular or landline) for the duration of the study with the ability to receive calls
- The ability to send and receive email messages (required) and text messages (optional)
- English or Spanish speaking and reading

Exclusion Criteria

- Patients who are unable or unwilling to provide informed consent to participate will be excluded

from the study.

- Examples may include but are not limited to patients who present with acute or chronic cognitive impairment that would preclude their ability to consent (i.e. acute psychosis, intoxication, or intellectual disability).
- Patients who are inappropriate for study participation based on provider clinical judgement.

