6.2 Recruitment Strategy

SLHS routinely screens patients 12 years of age and older for suicide risk in EDs and primary care clinics. Patients who screen positive using the C-SSRS should complete a safety plan (moderate to high risk/provider judgment) or a connection and support plan (low risk/provider judgment) with a provider or clinical staff as part of standard of care. Following safety planning or connection and support planning, based on clinical judgment, patients should be introduced and invited to participate in the SPARC Trial by the provider or staff and may be given a brief hand-out describing the study. If the patient is interested in learning more, a video visit with a centrally-located Research Coordinator will be ordered through Epic or a phone call will be initiated to conduct informed consent and study enrollment.

Additionally, patients who express interest in the study but are unable to complete study enrollment and informed consent while in the clinic or ED may agree to be contacted by a Research Coordinator after they leave SLHS. In this case, study staff may contact the potential participant to review eligibility criteria, answer questions and gain informed consent. Study staff will reach out via text or email as soon as possible within 3 business days of the clinic or ED encounter to invite the potential participant to schedule a phone call or video visit. An opt out option (such as STOP or NONE) will be provided for individuals who do not wish to proceed, and the study team will not call potential participants who have not responded in writing to express interest in continuing. Study enrollment and informed consent will be conducted using videoconference or telephone to connect patients to centrally located study staff. All staff conducting informed consent and study enrollment will be trained in human subjects' protection and study procedures and will be delegated to do so by the study PI.

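### The emergency department comparison of nurse-administered and self-completed C-SSRS scores (Protocol 9.2) cannot be read as an effect of administration mode

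*Protocol*

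**What the plan says.** Section 9.2 describes two C-SSRS scores at baseline for ED participants. The first is the clinical screen: "In EDs, C-SSRS screening is routinely administered by nurses during triage as standard of care". The second is the same instrument, "administered in a self-complete format for study participants as part of their baseline surveys". The protocol then plans that "The two C-SSRS scores collected during the baseline visit in EDs (nurse-administered vs. self-administered) will be compared as a sub-analysis", looking for systematic differences, and adds: "The results of this sub-analysis may inform future clinical practice as it relates to C-SSRS administration in SLHS EDs and other settings".

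Four other provisions fix who contributes a pair of scores and in what order:

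- The nurse's score selects. Section 9.2: "The C-SSRS delivered as standard of care in either setting will be used as the basis for determining eligibility". The entry rule in 6.1.2 is: "Positive screen for suicidal ideation or behavior using C-SSRS (any C-SSRS score >0), or current /most recent visit is related to suicide attempt".
- A completed safety plan or connection and support plan is itself an inclusion criterion (6.1.2), so it precedes enrolment.
- The baseline survey is filled in after enrolment and consent (13.1).
- Enrolment need not happen in the ED. Under 6.2, patients who cannot enrol on site "may agree to be contacted by a Research Coordinator after they leave SLHS", with first outreach within 3 business days.

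**The concern.** A comparison of modes needs the same people scored both ways, with neither score deciding who is in the sample and with order balanced or irrelevant. Here the nurse's score decides entry, the order is always nurse then self, and a clinical intervention and sometimes days lie between the two. Mode is therefore fully confounded with order, planning and elapsed time, and one of the two measurements is truncated by the entry rule.

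At stake is a side conclusion, not the trial's main result. Section 9.2 intends the comparison to guide how EDs administer a suicide screen. A gap produced by selection could be taken as evidence that patients report less on self-completion than to a nurse. The reverse question, whether nurse triage misses patients who would disclose on self-report, cannot be answered, because patients who score 0 with the nurse are not re-scored unless they enter through an attempt-related visit. No later analysis can recover those scores.

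**Working it through.** The protocol gives no figure for this sub-analysis, so there is nothing to reproduce. The check asks what gap would be expected if mode, order and time had no effect.

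**Inputs from the protocol.** Scores run from 0 to 6, by highest item answered yes (9.2.1, Appendix A). Entry is by first score above 0, or by an attempt-related visit (6.1.2). The share screening positive is 2% of adults and 6% of adolescents, pooled over EDs and primary care (9.1.1). No ED-only rate is given.

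**Assumed inputs.** Latent correlation between the two administrations, 0.99 down to 0.70; the mix of scores among positives; and 30% positive as a much higher ED rate.

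**Step 1: identity.** Let X1 be the nurse score and X2 the self-completed score. With no effect of mode or time the two are exchangeable, so E[X2 − X1] = 0 over everyone screened. Splitting on the first score and rearranging gives

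E[X2 − X1 | X1 > 0] = −E[X2 | X1 = 0] × P(X1 = 0) / P(X1 > 0).

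This is below 0 whenever anyone scoring 0 first would score above 0 second. The multiplier is 0.98/0.02 = 49 at 2% positive, 0.94/0.06 = 15.7 at 6% and 0.70/0.30 = 2.3 at 30%. A mean second score of only 0.01 among screen-negatives gives a gap of −0.49 at 2% and −0.16 at 6%.

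**Step 2: simulation.** Three million pairs; bivariate normal severity with correlation r; identical cut-points to scores 0–6; selection on first score above 0; assumed mix among positives of 22, 26, 15, 12, 7 and 18% for scores 1 to 6 (mean 3.1). Expected self-minus-nurse gap in points:

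| r | 2% positive | 6% positive | 30% positive |
|---|---|---|---|
| 0.99 | −0.19 | −0.14 | −0.07 |
| 0.95 | −0.58 | −0.44 | −0.21 |
| 0.90 | −0.97 | −0.74 | −0.36 |
| 0.80 | −1.53 | −1.23 | −0.62 |
| 0.70 | −1.94 | −1.60 | −0.86 |

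At 6% and r = 0.90, other mixes (mean 2.64 or 3.60) give −0.61 and −0.91. If everyone screened were scored twice, the expected gap would be 0.

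**Step 3: the attempt-visit route.** A patient admitted for an attempt with a first score of 0 can only stay or rise. If a share f of the ED sample is of this kind, with mean second score m, the selection gap g is cancelled when f = |g| / (m + |g|). For g = −0.3 and m = 2, 4 or 6, f is 0.3/2.3 = 13%, 0.3/4.3 = 7% or 0.3/6.3 = 5%. For g = −1.0, f is 1/3 = 33%, 1/5 = 20% or 1/7 = 14%.

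**Step 4: a further filter.** Enrolment also passes through a plan completed with staff and a provider's judgement, which may remove some triage false positives. Adding one independent confirming assessment to the model (6% positive) cuts the gap from 0.74 to 0.50 at r = 0.90 and from 0.14 to 0.08 at r = 0.99. The bias shrinks but stays.

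**The case against.** The best defence is that this is an unpowered, descriptive side comparison supporting no aim or primary or secondary outcome. The protocol speaks only of systematic differences that may inform practice. It states no causal mode estimate and makes no claim about sensitivity or missed cases. Handling of elapsed time and pair types would normally sit in a statistical analysis plan. This stands as to severity. It does not rescue the stated use: the intended application is to C-SSRS administration, and the missing nurse-negatives are a matter of sampling that no analysis plan can repair.

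Four stronger readings are tempting, and the documents do not support them.

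- A reader might infer that self-completed scores are bound to come out lower. Attempt-visit entrants with a first score of 0 pull the other way, and a true upward mode effect could mask the bias.
- A reader might infer that safety planning lowers the second score. No direction is documented. Appendix A prints look-back wording (ever; past 3 months), which a plan does not change, and the suicide narrative that opens safety planning could raise or lower disclosure.
- A reader might take the tabulated gaps as the expected size. They rest on an unstated reliability and on pooled positive rates. At near-perfect repeatability the gap is small.
- A reader might set the gap against the 1-unit difference in 14.2. That is a between-arm figure. The ED self-completed baseline is taken in both arms alike, so the randomised comparison is not biased by this.

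**Conclusion.** The point holds as a minor one. The planned comparison cannot isolate administration mode, because entry selects on one of the two scores and mode is inseparable from order, the intervening plan and, for some patients, days elapsed. For patients admitted by score, selection alone biases the self-completed mean downward unless answers are perfectly repeatable. For the whole ED sample the net bias is most likely downward but not certain.

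For correlations from 0.99 to 0.70 and the score mix above, the selection gap is about 0.1 to 1.6 points at 6% positive and 0.1 to 0.9 at 30%, before any offset from attempt-visit entrants and before any further clinical filtering. The existence of the bias needs only imperfect repeatability; its size needs the assumptions listed. Under-detection by nurse triage cannot be assessed in this sample.

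**What to change.** In 9.2:

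1. Describe the sub-analysis as a descriptive comparison of the triage screen with a later, post-plan self-completed score among patients selected on the triage screen. Say that it is neither a mode effect nor a change over time. Calling it change would invite reading regression to the mean as improvement after planning.
2. Report pairs from the same visit separately from pairs completed after departure. Table 4 already lists encounter dates and times, and the survey is completed in REDCap, whose completion time is assumed to be available.
3. State that the first score is truncated by the entry rule except for attempt-related visits, and that nurse-negative patients are otherwise absent, so neither sensitivity nor under-detection can be estimated.
4. Delete the sentence that the result may inform C-SSRS administration.

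Restricting a mode claim to the behaviour item would not solve the problem, because that item also feeds the score that selects.

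The cost is a few lines of protocol text and one split table. What is given up is one side claim that these data cannot support.

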9.2.1 Scoring the C-SSRS

The C-SSRS lifetime-recent screener score is determined based on the highest question number (1-6) to which a participant responds “yes”. For example, a score of 5 would be assigned to a participant who responded “yes” to Question 5 and any or all preceding questions. Please consult *Appendix A* of this protocol for additional C-SSRS scoring criteria. The additional items related to suicide attempts and lethal means will not be included in the C-SSRS score but will be compared across intervention groups.

9.3 Secondary Outcomes & Assessment

Secondary outcomes include reduced loneliness, increased uptake of outpatient mental health services, and reduced return to care for suicidality.

9.3.1 Loneliness

Loneliness is a well-established risk factor for suicide,⁷⁰⁻⁷² depression,⁷³⁻⁷⁶ psychological stress,^{76,77} and anxiety.^{73,74,77} Loneliness will be measured at baseline, 6 and 12 months using the NIH Toolbox Social Relationship Scales Loneliness measure. The NIH Toolbox is a comprehensive set of neuro-behavioral measurements that quickly assess cognitive, emotional, sensory, and motor functions.⁷⁸ The measurements were developed to be versatile, brief, and psychometrically sound.⁷⁸ The NIH Toolbox is composed of multiple batteries, one of which is the NIH Toolbox Emotion Battery. The Emotion Battery is comprised of four different domains, including the Social Relationship Scales which have items that have been validated to measure loneliness.⁷⁹ The loneliness measure of the NIH Toolbox Emotion battery for adults 18+ is comprised of five items with rating scale responses of never, rarely, sometimes, usually, and

always. Responses are then used to calculate a raw score which is converted to a t-score 99. The version for adolescents 13-17 is comprised of 7 items. Both measures were validated using confirmatory factor analysis.⁷⁹

9.3.2 Uptake of Outpatient Mental Health Services

Uptake of outpatient mental health services will be measured at 6 and 12 months in two ways: through self-report, and (wherever possible) directly via electronic health records or using internal claims data.

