1.2 Schema / Study Flow Diagram

Figure 1: SPARC Trial Flow Diagram

2. Research Question & Specific Aims

Research Question: What is the best brief suicide prevention intervention for adults and adolescents who screen positive for suicidal ideation or behavior in emergency departments or primary care clinics?

Specific Aims.

- **Aim 1:** Compare the effectiveness of two brief suicide prevention interventions (safety planning intervention or connection and support planning plus structured follow-up from a suicide prevention hotline (SPI+), versus safety planning intervention or connection and support planning plus caring contacts (SP+CC)) to (a) reduce suicidal ideation and behavior, (b) reduce loneliness, (c) reduce return to care for suicidality, and (d) increase uptake of outpatient mental healthcare services over 12 months among adult and adolescent patients screening positive for suicide in emergency departments (EDs) and primary care clinics.
 - **Aim 1 Hypothesis:** We hypothesize that compared to SPI+, SP+CC will result in lower levels of suicidal ideation and behavior, reduced loneliness, reduced return to care for suicidality, and an increase in uptake of outpatient mental healthcare services for adults and adolescents screening positive for suicide.
- **Aim 2:** Assess the acceptability of connection and support planning and the safety planning intervention, with or without follow-up among providers and clinical staff in EDs and primary care clinics.
- **Aim 3:** Assess the acceptability of SPI+ and SP+CC among adult and adolescent patients.

3. Introduction

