6.4 Populations for Analyses

Analyses will be completed using the following populations:

1. **Intention to Treat (ITT) Analytic Population:** Data for all participants that complete study enrollment will be included in this dataset.
2. **Safety Analysis Population:** The dataset shared with the Data & Safety Monitoring Board for safety analysis will include data for all participants who completed study enrollment (e.g., the ITT Analytic Population Dataset).
3. **Per-Protocol Analysis Population:** Data for a subset of participants who were retained for the duration of the study and completed the minimum assigned intervention (e.g. received at least one phone call (SPI+), or were sent at least 4 caring contacts (SP+CC)).
4. **Additional Populations:** Additional datasets may be developed to complete sensitivity analyses, for example, where missing data have been imputed using different techniques.

7. Study Procedures

Pre-Consent – All participants (All activities are standard of care)

- C-SSRS screening for suicide risk at clinic or ED visit
- Development of safety plan or a connection and support plan

Baseline / Enrollment Visit – All participants (During/following clinic or ED visit)

- Study enrollment and informed consent
- Baseline Survey
 - Baseline survey includes questions related to demographics, socioeconomic status, gender identity, sexuality, religion, drug and alcohol use, quality of life, loneliness, self-harm and suicidal behavior.

Follow-Up Intervention – SPI+ participants

- Follow-up phone calls from the Hotline
 - 1 call within 72 hours of study enrollment to connect with the participant.
 - Series of 1-6 phone calls, based on participant's preference.
 - See *Description of Interventions*.

Follow-Up Intervention – SP+CC participants

- Follow-up phone call and caring text or email messages from the Hotline
 - 1 call within 72 hours of study enrollment to connect with the participant.
 - 25 personalized caring text or email messages sent according to a standardized schedule over a 12-month period.
 - See *Description of Interventions*.

2-Week Patient Satisfaction Survey – All participants (REDCap survey link sent via text or email)

- Patient satisfaction survey related to intervention received

6 Month Outcome Assessment – All participants (+ 4 weeks variance window) (REDCap survey link sent via email or text, or phone call)

- 6-Month Outcomes Survey

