 - Outcomes survey includes loneliness, suicide risk, self-harm and suicidal behavior, behavioral health treatment.

12 Month Outcome Assessment – All participants (+ 4 weeks variance window) (REDCap survey link sent via email or text, or phone call)

- 12-Month Outcomes Survey
 - Outcomes survey includes loneliness, suicide risk, self-harm and suicidal behavior, behavioral health treatment, and patient satisfaction.

Assessing Provider Satisfaction (Aim 2)

Providers and staff in study sites will be emailed an invitation to complete a survey during year 1 or 2 of the study. Providers and staff will complete surveys using a REDCap link delivered via email. A statement will be included in the survey invitation email indicating that opening the link and completing the survey constitutes provider/staff consent to participate in the survey. These surveys will be confidential and no personal health information will be collected.

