9.3.4 Assessing Bias in Self-Reported Measures

In addition to self-reported uptake of care, for patients referred to a provider within SLHS, study staff will measure whether they attended one or more outpatient mental healthcare appointments or returned to care (ED utilization) for suicidality by looking at their electronic medical record in EPIC, reviewing an ED dashboard/EDIE System and by utilizing claims data when possible. However, we do not anticipate having complete data for patients who see a provider outside of SLHS. For these participants, study staff may review data in EPIC Care Link, or via other means to measure uptake of outpatient mental health treatment. Discrepancies are expected between data on uptake of treatment and care-seeking related to suicide from self-report compared to the data that can be directly measured. The analytic team will estimate the extent and direction of bias in a sub-set of participants from each comparator group who were referred to an SLHS provider by comparing self-reported uptake of outpatient mental healthcare services with what is recorded in EPIC. This will allow estimation of the degree of bias present in the self-reported data and determination of whether the extent of bias differs between the two comparator groups.

10. Description of Interventions

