10.2 Safety Planning Intervention Plus Phone-Based Follow-Up (SPI+)

The Safety Planning Intervention (SPI+)¹⁻⁷ includes safety planning plus a structured telephone-based intervention following discharge from the emergency department or departure from a primary care clinic. For the SPARC Trial, Hotline follow-up specialists will call participants within 72 hours of study enrollment to (1) conduct a brief suicide risk assessment; (2) review and revise the participant’s connection and support plan or safety plan; and (3) provide support with treatment engagement, if indicated. Participants will receive at least one and optional additional phone calls as part of the SPI+ follow-up intervention generally delivered according to the following schedule: days 3, 7, 14, 30, 60, 90.^{8,9} Modifications may be made to the schedule due to weekends, holidays, or participant availability, and additional calls may be scheduled as desired by the participant. The follow-up will stop once the participant is successfully engaged in outpatient treatment or does not desire further follow-up support. In instances where participants cannot be reached for an initial phone call within 72 hours, Hotline staff will continue to attempt to schedule and complete the phone call. A minimum of three attempts to schedule and complete each phone call will be made.

This version of the intervention differs from the Stanley/Brown SPI+ model in that the structured follow-up

will be conducted by Hotline follow-up specialists, rather than by specially trained social workers or psychologists. In this pragmatic clinical trial, we are committed to testing a model that could be feasibly scaled up and replicated in other rural and resource-limited settings. The schedule was adopted from similar military follow-up programs: the Marine Intercept Program⁹ and the Navy Sailor Assistance and Intercept for Life (SAIL) Program.⁸ We selected this schedule given that we wanted to offer a longer follow-up window than the traditional SPI+ in order to support treatment engagement because connecting with outpatient behavioral health treatment (such as a counselor or therapist) typically takes 4-6 weeks for patients at low risk for suicide in our health system.

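### Outpatient mental health care already under way at enrolment is not recorded at baseline, so Aim 1(d) cannot tell continuing care from new uptake and loses precision

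*Protocol*

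**What the plan says.** Protocol section 2 sets Aim 1(d) as a comparison of which follow-up will "increase uptake of outpatient mental healthcare services over 12 months". Section 9.3.2 fixes the time points: "Uptake of outpatient mental health services will be measured at 6 and 12 months in two ways", namely self-report and, where possible, health records or internal claims.

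The only text close to a scoring rule is in section 9.3.4. For patients referred within the health system, "study staff will measure whether they attended one or more outpatient mental healthcare appointments", using Epic, the ED dashboard and claims where possible. The same section accepts that data on care outside the system will be incomplete.

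Section 7 lists the content of the surveys:
- Baseline: "Baseline survey includes questions related to demographics, socioeconomic status, gender identity, sexuality, religion, drug and alcohol use, quality of life, loneliness, self-harm and suicidal behavior".
- 6 and 12 months: "Outcomes survey includes loneliness, suicide risk, self-harm and suicidal behavior, behavioral health treatment".

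Treatment is thus asked about at follow-up but is not in the listed baseline content. Section 9.1 (exposure variables) and the baseline exposures in Table 4 do not list it either. The nearest items in Table 4 are antidepressant and lithium use, and behavioral health referrals. Section 9.2 says in general terms that outcomes are measured at baseline, but names only suicide risk and loneliness. Section 6.1.2 describes the inclusion criteria as broad, and no criterion excludes a patient already in treatment.

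**The concern.** Uptake in Aim 1(d) reads most naturally as a connection to care that follows enrolment. Section 10.2 supports that reading: it explains the length of the SPI+ schedule by the time it takes to connect with outpatient treatment. A participant who already sees a therapist and continues to do so will report treatment at 6 and 12 months in either arm. Without a baseline record, that participant looks the same as one who started care after the index visit.

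Two things are at stake. The estimated difference describes a mixture of continuing and new care, and is smaller than the difference among those who could newly start. A strong predictor of the outcome, fixed before randomization, is also unavailable for adjustment. A small or null result on Aim 1(d) would then be hard to interpret. An analysis plan can define uptake, but it cannot supply a baseline answer that was never asked for.

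**Working it through.** **No figure of the plan to reproduce.** Section 14.2 powers the primary outcome only. The protocol states no uptake rate, effect size or power for this outcome.

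**Inputs from the protocol.** Adults 790, adolescents 592, dropout up to 30% (section 14.2); two-sided alpha 0.05 (section 14.1).

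**Assumptions, not in the documents.** Equal arms; uptake of 50% versus 60% among those not in care at enrolment; a share p already in care in each arm; all of that share still in care at follow-up.

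**Evaluable adults per arm:** 790 × 0.7 / 2 = 276.5.

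**Dilution.** Observed rate = p + (1-p) × rate among those not in care, so the observed difference is (1-p)d. At p = 40%: 0.4 + 0.6 × 0.5 = 70% and 0.4 + 0.6 × 0.6 = 76%, a difference of 6 points instead of 10.

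**Power, baseline care ignored (p = 40%).**
- SE = √[(0.70 × 0.30 + 0.76 × 0.24) / 276.5] = 0.0377
- Power = Φ(0.06 / 0.0377 - 1.96) = Φ(-0.37) ≈ 36%

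**Power, restricted to those not in care (p = 40%).**
- n per arm = 276.5 × 0.6 = 165.9
- SE = √[(0.50 × 0.50 + 0.60 × 0.40) / 165.9] = 0.0543
- Power = Φ(0.10 / 0.0543 - 1.96) = Φ(-0.12) ≈ 45%

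**Power, all participants, stratified by baseline care (p = 40%).** In the in-care stratum everyone counts as uptake in both arms, so its difference and its variance are zero. The stratified difference is 0.6 × 0.10 = 0.06 with SE 0.6 × 0.0543 = 0.0326. The ratio is again 1.84, so power is again about 45%. The gain does not require dropping anyone.

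**Over a range of p (adults):**

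| p | Observed rates | Difference | Power, baseline care ignored | Power, baseline care used |
|---|---|---|---|---|
| 0% | 50% vs 60% | 10 points | 66% | 66% |
| 20% | 60% vs 68% | 8 points | 50% | 57% |
| 40% | 70% vs 76% | 6 points | 36% | 45% |
| 50% | 75% vs 80% | 5 points | 29% | 39% |

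**Sensitivity.**
- Adolescents (592 × 0.7 / 2 = 207.2 per arm), p = 40%, same formulas: about 28% ignored, 36% used.
- Adults with assumed uptake of 30% versus 42%, p = 40%: observed 58% versus 65.2%; about 41% ignored, 63% used.
- Adults, 50% versus 60%, p = 40%, but only 90% of those in care remain so in both arms: observed 66% versus 72%, SE 0.0393, power about 33% ignored. Stratified SE = √[0.4² × 2 × 0.9 × 0.1 / 110.6 + 0.0326²] = 0.0364, power about 38%. The gain shrinks as baseline care predicts later care less well.

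**The case against.** Four objections have force.

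- **The scoring rule is not stated.** A reader might infer that the protocol counts any visit as uptake. The one-or-more wording comes from section 9.3.4, where it describes a record check for patients referred within the health system. The self-report item is not shown, and an operational definition may properly sit in the analysis plan. What remains is narrower: care at enrolment is not among the data to be collected.
- **No bias between arms.** A reader might infer that existing care hides the effect or makes a false null likely. Patients are individually randomized, so prior care is balanced on average and the all-participant contrast is a valid intention-to-treat comparison. The loss is dilution and precision. Under the 50% versus 60% assumption, adult power is only 66% even with nobody in care, so a null could not be put down to this gap alone.
- **Partly recoverable.** A reader might infer that nothing can be done afterwards. Table 4 already holds record numbers, encounter dates and providers, so care within the health system can be sought by look-back. No look-back is planned, and care outside the system would still depend on an answer given at enrolment.
- **Restriction is a choice of estimand.** SPI+ calls include support with treatment engagement, so follow-up might affect whether someone with existing or lapsed care stays or returns. Making those not in care the main population would discard that. Keeping everyone and adjusting is as defensible and, in the calculation above, as precise.

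Section 10.2 also says of SPI+: "The follow-up will stop once the participant is successfully engaged in outpatient treatment". This is part of how that arm is defined. It means the number of calls may depend on care status, but it does not show that uptake is mismeasured.

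**Conclusion.** The gap is real and modest. The protocol asks about treatment at 6 and 12 months, plans no baseline counterpart and admits patients already in treatment, so continuing care cannot be told from new uptake. The risk difference shrinks by the factor (1-p). At p = 40% with 50% versus 60% uptake among the rest, adults have about 36% power ignoring baseline care and about 45% using it. These sizes rest on assumed p, assumed uptake rates, equal arms and full retention in care; the documents supply none of these. The direction (a smaller difference, and precision recoverable by using baseline care) holds in every scenario checked with p above zero. The documents do not support a claim of bias between arms, of an irreparable dataset or of a likely false conclusion. This is a cheap improvement to a secondary outcome.

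**What to change.** - Add to the Table 4 baseline variables any outpatient mental health care before the index visit, taken by a fixed look-back in Epic and claims. These are already sources for this outcome, and the field can be filled in retrospectively for participants already enrolled.
- Add one baseline-survey item on current outpatient mental health treatment.
- Keep the all-participant comparison for Aim 1(d), adjusted for or stratified by baseline care.
- Pre-specify uptake among participants not in care at baseline as a supporting analysis.

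The cost is one survey item and a slightly wider query. Prior care outside the health system will rest on self-report, and for participants enrolled before the change it may be missing.
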